This trial aims to deliver, across a range of UK hospitals, a package of interventions for Acute Kidney Injury (AKI) aimed to improve recognition and quality of care for AKI, and to assess how this translates into better outcomes in AKI patients and if this intervention can reduce the incidence of h-AKI (detailed protocol available on request).

For practical reasons this service can only be applied at the level of the population covered by the hospital and not on a subset of random patients within a hospital. Also the intervention is assumed to have a positive effect on AKI management/outcomes. For these reasons the study has been set up as a stepped-wedge cluster randomised trial (SWCRT), with the intervention applied at a cluster level and applied to all participating units by the end of the study. Such an approach overcomes any ethical problem of withholding a treatment considered likely to be effective, as the entire population recruited will receive the treatment by the end of the study. This approach also allows for differentiation between the effect of the intervention and potential independent unknown time-related factors.

There are no reporting guidelines specific to SWCRTs, so this Statistical Analysis Plan (SAP) is written to be consistent with the extension to cluster randomised trials of the CONSORT 2010 document [Campbell et al., 2012] and further suggestions recently published for SWCRT [Hemming et al, 2015]. This statistical analysis plan will guide the Trial Statistician during the statistical analysis of all quantitative outcomes in order to answer the objectives of the study.

STUDY DESIGN

A Stepped Wedge Cluster Randomised Trial approach will be taken. This means that the intervention will be delivered in sequential steps to one or more units of randomisation per time-period and

delivered to all the units of randomisation by the end of the study. This study has recruited 5 hospitals and is planned to take two years, between December 2014 and November 2016, with 2 initial control periods for all 5 hospitals, followed by 5 steps of randomisation (one hospital per step), and including a transition period (the first 'treatment period', when the treatment is expected not to have reached full efficacy on outcomes), for a total of 8 time-periods, each of 3 months in length (24 months in total – see Table-1, page.6).

THE INTERVENTION

The intervention (protocol, sections 3 and 5, available on request for details), has 3 parts:

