- 4. Length of hospital stay of patients with AKI (patient level data, counts in days, potentially to analyse using Poisson model, depending on the distribution of this outcome)
- 5. Number of critical care bed days used by patients with AKI (patient level data, counts of days in ICU for each patients, possibly to analyse using Poisson or negative binomial model zero inflated, depending on distribution, as many counts of zeros are expected.
- 6. Achievement of complete renal recovery by hospital discharge in AKI patients (with renal recovery defined as serum creatinine returning to a value less than 27 μ mol/l above baseline creatinine value). These are patient level data, binary outcome on all AKI patients (0=did not recover during hospitalisation; 1=recovered during hospitalisation, logistic analysis).

RANDOMISATION UNITS AND TIME-PERIODS

In this trial, the primary outcome will be measured for each episode of AKI detected in patients hospitalised overnight, while the intervention will be implemented at hospital level. Hence this is a cluster randomised trial, where the units of randomisation are the participating hospitals.

In this trial the intervention will be implemented in a total of 5 hospitals, with only one hospital being randomised each time at each step (with a total of 5 randomisation steps), with time periods of 3 months length.

This intervention is complex and would take some time to deliver it. While the electronic detection system has been set up in advance (with results kept suppressed at baseline) and can be activated immediately at start of intervention, teaching to staff will require some time as well as change in practice to be established. For these reasons we expect to observe no quantifiable effects on the outcomes of AKI patients at first after intervention, and hence we have planned to have a transition period. While data on primary and secondary outcomes will be collected for all periods of the study, data from the transition period for each hospital will be excluded from the analyses. As this trial has sufficient power, we have planned for the transition period to be of the same length as the unexposed/exposed time-periods (3 months).

In summary (see Table-1), we are planning to have, for each hospital, two or more control periods (unexposed to the intervention, coded as '0'), one transition period (the first period of intervention,

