The annual number of hospital admissions in the 5 institutions recruited was taken from HSCIC (total annual admissions of about 434,000). We used a conservative assumption of AKI incidence of 2.5% of admissions and 30-days mortality rate after AKI of 16% [Selby 2012], which corresponds to an average of AKI episodes per hospital per 3 months of about N=540. Power was set at 80%, alpha at 0.05 and a range of values for inter class correlation (ICC) between 0.01-0.2 was considered. For the sample size calculations we used a Stata program [Hemming and Girling, 2014], which can accommodate for the transition periods. This showed that with a trial study-time of two years (Dec'14 – Nov'16) using the 5 units, with one unit per randomisation step and with one transition period (as in table-1), we would be able to detect a decrease in mortality from 16% to 12.8%. This corresponds to a reduction of about 20% in 30-days mortality, which is both clinically relevant (equating to around 300 fewer deaths each year for the total of the 5 units) and plausible.

RECRUITMENT AND RANDOMISATION

- Eligibility of hospitals

Considering this trial was starting in parallel to the AKI national program (with the need to temporarily exempt the hospitals recruited) and the knowledge that the numbers of AKI episodes in hospitalised patients are fairly high, we planned to limit the recruitment to only 5 hospitals. For convenience the following 5 units were recruited, 2 from Surrey (Ashford and Frimley Park) and 3 from Yorkshire (Bradford, Leeds General and Leeds St. James).

- Eligibility of patients

Adult patients (≥ 18 yrs) hospitalised overnight in the participating hospitals are eligible if they should present in hospital with AKI or develop an episode of h-AKI, during the study period. In particular, AKI will be identified by having an inpatient blood test that triggers an AKI warning stage result, using the NHS England AKI detection algorithm (<http://www.england.nhs.uk/wp-content/uploads/2014/06/psa-aki-alg.pdf>), both in the control/baseline periods (when results are suppressed, not visible to end-users) and implementation periods.

Patients that are identified as having AKI but were already on chronic dialysis are not eligible and will need to be excluded, while patients with a renal transplant are eligible.

The five hospitals were recruited and the randomisation took place on the 11th of May 2015.

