The primary outcome (30 day mortality) is the only outcome that will be observed in a fixed time interval starting at date of admission rather than during the hospitalisation spell. While some hospitalisation spells will last one month or more, most will be shorter. As we have previously pointed out, multiple episodes (hospitalisations with AKI) in the same patient can occur. This is not a problem when the outcome is related exclusively to the hospitalisation spell (duration, ICU, recovery, progression). However in the analysis of 30 day mortality the presence of multiple episodes could create a problem, if the multiple episodes should occur within a month. For example a patient could be hospitalised with AKI for a week, return at home and re-hospitalised a second time after a week, and die in hospital after few days, in which case the patient will be present twice in the cohort, both times with an outcome of death within 30 days. For this reason, only in this analysis, we will exclude repeated AKI-episodes that occur within a month from the previous hospitalisation, whichever the outcome. A case like the one just described will appear only once in the dataset, while a patient that is hospitalised with AKI for a week, then is back at home for 4 weeks, and then re-hospitalised with AKI again will appear twice.

Analysis of 30-day mortality will be done using a mixed-effects logistic regression, as a patient level analysis, and accounting for correlations between episodes in the same hospital by including hospital in the model as a random effect. If a non-insignificant proportion of episodes of AKI should be multiple episodes in same patients, we will also account for the correlation between episodes in the same patient by fitting a second random effect for patient in the analysis. The primary outcome response

will be binary (patient died by 30days after AKI=1, patient still alive after 30days since AKI=0). Mortality is expected to decrease after the intervention.

The odds ratio estimate of the mortality risk for the treatment effect (intervention versus control) with 95% confidence interval will be presented (Model-1). Analysis will be adjusted by time-period (step) (Model-2) and individual patients' characteristics (Model-3) such as age at hospitalisation, gender, possibly ethnicity, and Charlson comorbidity score.

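### The primary model and the power calculation leave no room for hospital-specific quarterly variation; if there is any, the planned 95% CI is too narrow and power is below the stated 80%

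*SAP*

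**What the plan says.** In the SAP's Analysis of primary outcome, 30-day mortality is analysed by mixed-effects logistic regression, "accounting for correlations between episodes in the same hospital by including hospital in the model as a random effect". The Model building notation has one random term for the hospital, indexed by hospital only. The period effect is fixed and common to all hospitals, and may be categorical or linear. The only second random effect foreseen is for the patient. Model 4 adds a time-since-exposure effect, again common to all hospitals. Model 3 is named as the primary result, and its odds ratio is to be reported with a 95% CI. No reference distribution, degrees of freedom, robust variance or permutation test is named.

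The Sample size calculation section gives "an average of AKI episodes per hospital per 3 months of about N=540" and says: "Power was set at 80%, alpha at 0.05 and a range of values for inter class correlation (ICC) between 0.01-0.2 was considered". It concludes that "we would be able to detect a decrease in mortality from 16% to 12.8"%. The method is given as "For the sample size calculations we used a Stata program" that can handle the transition periods. One ICC is the only correlation input mentioned. Under Randomisation units and time-periods, "data from the transition period for each hospital will be excluded from the analyses".

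**The concern.** The treatment effect in Models 2 to 4 is estimated from how each hospital's mortality changes relative to the other hospitals in the same quarters. A constant hospital intercept treats every such departure beyond binomial noise and the covariates as zero. It also assumes that two episodes in one hospital are equally correlated whether they fall in the same quarter or two years apart.

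The SAP itself gives reasons to expect local change over time. It mentions imbalance across hospitals and steps (Descriptive statistics), growing staff experience, fading enthusiasm and untrained new staff (Analysis of primary outcome), and, for incidence, laboratory re-organisation at individual hospitals (Data from hospitals). The shared period effect does not absorb change that is specific to one hospital.

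At stake are the CI and p-value of the single primary result. If the omitted variance is not zero, ordinary local fluctuation is partly read as treatment effect, and the error runs towards false claims of benefit or harm.

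**Working it through.** **Inputs from the SAP.** Five hospitals, eight quarters, one hospital per step, two all-control quarters, transition quarter dropped: 35 hospital-quarters, 20 control and 15 exposed. Episodes per cell: 434,000 × 0.025 / 5 / 4 = 542.5, taken as 540. Mortality 16% against 12.8%, a difference of 0.032. Alpha 0.05, taken as two-sided because the SAP does not say. The layout is the one in the text (control until transition); Table-1 as it reads here shows exposed quarters before the transition in rows B to E, which does not fit that text.

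**Formula.** Total variance at the average risk of 0.144 is 0.144 × 0.856 = 0.1233. Of this, ICC × 0.1233 lies between hospitals. With autocorrelation r, a share (1 − r) of the between-hospital part is specific to the quarter:

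- quarterly variance: σ²q = 0.1233 × ICC × (1 − r)
- sampling variance of a cell: σ²e = 0.1233 × (1 − ICC) / 540
- SE of the treatment effect ≈ √[0.6 × (σ²q + σ²e)]. The factor 0.6 is the inverse of the treatment indicator's residual sum of squares (1.667) after hospital and categorical period over the 35 cells.
- power = Φ(0.032 / SE − 1.96)

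The tabulated results use full generalised least squares with a random intercept. It agrees with this shortcut to within about 1 point of power.

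**Reproducing the stated 80% (r = 1, no quarterly variation).** At ICC 0.05, σ²e = 0.1233 × 0.95 / 540 = 0.000217 and SE = √(0.6 × 0.000217) = 0.0114. Power is Φ(2.81 − 1.96) = 80%. Full results are 79.0, 80.2, 82.2 and 86.4% at ICC 0.01, 0.05, 0.1 and 0.2. If 0.1233 is instead taken as the within-hospital variance, power is 78 to 79% throughout. On neither reading does a larger ICC materially lower power.

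**Adding quarterly variation (assumed values).** At ICC 0.2 and r = 0.99, σ²q = 0.1233 × 0.2 × 0.01 = 0.000247 and σ²e = 0.1233 × 0.8 / 540 = 0.000183. Then SE = √(0.6 × 0.000430) = 0.0160 and power is 51%. The planned model reports √(0.6 × 0.000183) = 0.0105, so its nominal 1.96 is in truth 1.96 × 0.0105 / 0.0160 = 1.28, a type I error of 20%.

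| r | ICC | Quarterly SD (points) | Power, correct SE | Type I error, planned model |
|---|---|---|---|---|
| 0.99 | 0.01 | 0.35 | 76.9% | 5.6% |
| 0.99 | 0.05 | 0.79 | 69.8% | 8.4% |
| 0.99 | 0.1 | 1.11 | 62.6% | 12.1% |
| 0.99 | 0.2 | 1.57 | 51.4% | 20.1% |
| 0.95 | 0.01 | 0.79 | 69.0% | 8.2% |

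With the quarterly SD set directly at ICC 0.05:

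| Quarterly SD (points) | Power | Type I error |
|---|---|---|
| 0.25 | 79.1% | 5.3% |
| 0.5 | 75.8% | 6.3% |
| 1 | 64.3% | 10.5% |

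The binomial SE of one cell is √(0.16 × 0.84 / 540) = 1.6 points, so quarterly variation of this order would be hard to see by eye.

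**Simulation check.** Logistic data, 3000 runs per setting, hospital as a fixed effect in place of the random intercept, no covariates. The z test's type I error was 5.2% with no quarterly variation, 6.4% at an SD of 0.62 points and 13.9% at 1.23 points. An overdispersion-corrected t test on 22 df gave 3.1, 3.5 and 5.1%.

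**The case against.** The strongest reply is that every harmful figure rests on a variance that the SAP does not give. On the SAP's own inputs the stated power is right, and at a quarterly SD of 0.25 points almost nothing changes. That stands. A reader might infer that the CI will be anti-conservative and that 80% power is not delivered; the documents support only the conditional statement.

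A reader might also infer that a normal approximation with five hospitals is itself the fault. The SAP names no reference distribution, so its use is an inference from silence. With zero quarterly variation the simulated z test held 5.2%. The small number of hospitals matters once a quarterly variance has to be estimated from 35 cells.

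Third, Model 3 adjusts for age, gender, Charlson score and possibly ethnicity, and categorical period absorbs shared seasonal change. Both may shrink the residual variation, and the calculations above do not include the covariates. This also stands, but covariates cannot be relied on to remove differences in staffing, training or practice.

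Finally, the worst figures need extreme settings. ICC 0.2 implies a between-hospital SD of √(0.1233 × 0.2) = 15.7 points. With r = 0.95 it implies a quarterly SD of 3.5 points, larger than the 3.2-point target effect. The 19.5% power calculated there should carry no weight. The 51% at r = 0.99 shares the extreme ICC, and marks the end of the SAP's own ICC range, not a likely value.

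**Conclusion.** The point holds in conditional form. The primary model and, as far as its single ICC shows, the power calculation have no term for hospital-specific quarterly variation. Any non-zero amount makes the planned CI too narrow and lowers power.

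The size is uncertain. It is negligible at a quarterly SD of 0.25 points. At the low end of the SAP's ICC range (0.01) with r = 0.95, it is a moderate loss to 69% power and 8% type I error. It becomes serious if the SD reaches 1 point or more. These figures assume a two-sided test, categorical time, equal cells of 540 and the layout in the text, and they take no account of covariate adjustment. The SAP's 80% is not an arithmetical error; what is missing is the condition on which it depends. The variance structure should be settled before outcomes are seen, because a later choice would be hard to defend.

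**What to change.** - **Model building:** add a hospital-by-period random intercept to Models 2 to 4. If the variation is absent, its estimated variance should be close to zero.
- **Inference:** name a small-sample reference distribution for the treatment effect. One choice with categorical period is t with 35 − 5 hospitals − 7 period contrasts − 1 treatment term = 22 df. With linear time the same count gives 35 − 5 − 1 − 1 = 28, so the df must follow the time coding chosen.
- **Sensitivity analysis:** report a permutation test over the 5! = 120 possible hospital orders, which matches how the sequence was randomised. Its smallest possible p-value is 1/120 = 0.008.
- **Sample size calculation:** state that 80% is conditional on no hospital-by-quarter variation, and show power for a range of autocorrelations. The hospitals are already randomised, so this changes interpretation and not conduct.

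The cost is SAP wording, slightly longer code, a somewhat wider CI and a less favourable stated power. Using 22 df alone takes power from 79.0 to 75.3% at ICC 0.01 and from 80.2 to 76.6% at ICC 0.05. In the simulation without quarterly variation, the overdispersion-corrected t test had 69.3% power against 77.1% for the z test.

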The as-treated analysis will include all cases of AKI as ‘control’ or ‘treated’ based on the treatment that patients had received at time of AKI episode, rather than the treatment they were assigned based on the allocation process. In this case 1st day of the month when e-alert was activated in each hospital will be considered the start of that hospital’s transition period.

The report will include adherence to the timing of randomisation to intervention.

NOTE: If a logistic model should not run/iterate then we will use an equivalent mixed-effects linear regression analysis, approximating by using 0 and 1 as a continuous variable for the dichotomous variable of 30 days mortality (Hussey and Hughes, 2007).

Analysis of secondary outcomes

- The aggregate-data secondary outcomes 1 and 3 (incidence of h-AKI and incidence of AKI by level of AKI - expressed as number of patients developing AKI per hospitalised population), will be analysed using a Poisson regression, standardised by age and gender and, if possible, by ethnicity.

This will be a cluster-level Poisson analysis, with one measure per time-period per hospital, if unadjusted (or one measure per time-period per hospital per age-gender subgroup, if standardised).

MODEL
$$\text{Log}(Y_{ij}) = \log(\text{exposure}_{ij}) + \theta * T_{ij} + \gamma_j + \alpha_i$$

Where Y_{ij} = count of AKI episodes in hospital I at time J

Exposure-ij=denominator, number of hospitalisations in hospital I at time J

θ = effect of the treatment variable (T=1 exposed, T=0 control) in centre I at time J

γ = effect of Time (vector if effect not linear)

(+ ωQ_{ij} in the model if we want to investigate interaction between Time and Treatment)

- For secondary outcome n-2 (progression of AKI, binary outcome), we will use the same analysis as for the primary outcome (mixed-effect logistic regression), limited to the cohort of episodes classified as level-1 and level-2 AKI at time of first detection.

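### The linear-regression fallback for 30-day mortality is not equivalent to the planned logistic model: it changes the effect measure to a risk difference and cannot give the promised odds ratio

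*SAP*

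**What the plan says.** In the SAP, Analysis of primary outcome plans a mixed-effects logistic regression of 30-day death with hospital as a random effect. A second random effect, for patient, is added if repeat episodes are common enough. On reporting it says: "The odds ratio estimate of the mortality risk for the treatment effect (intervention versus control) with 95% confidence interval will be presented". Under Model building, Model-3 (logit link, time-period, patient covariates, random hospital effect) is named as the primary result.

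The NOTE that ends this part reads: "If a logistic model should not run/iterate then we will use an equivalent mixed-effects linear regression analysis". It adds that death coded 0/1 is treated as continuous, calls this an approximation, and cites a stepped-wedge methods paper. It does not define failure to run, list any intermediate step, or say how the result would be reported in place of the odds ratio.

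Under Analysis of secondary outcomes, outcomes 2 (progression) and 6 (recovery) take the same analysis as the primary outcome, so they inherit the rule.

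**The concern.** The NOTE treats a change of link function as a computing detail. It changes what is estimated. The logistic coefficient is a log odds ratio, and the linear coefficient is a difference in percentage points. If Model-3 failed while Models 1 and 2 ran, the model-building sequence would mix two scales, with the primary result on the scale that was not promised.

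The linear model also uses one residual variance for all episodes, although a binary outcome has variance p(1-p), which differs between hospitals with different mortality.

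The remedy does not match the likeliest cause of failure either. It is a judgement and not something the SAP states, but the weak spots are the variance components: one estimated from five hospitals, and possibly one for patients who mostly have a single episode. Simplifying the random effects addresses that directly and leaves the scale alone. At stake is the meaning of the primary result if a convergence message appears after the data are in.

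**Working it through.** **Inputs from the SAP.** Sample size calculation: "total annual admissions of about 434,000"; 2.5% AKI incidence; "an average of AKI episodes per hospital per 3 months of about N=540"; mortality 16% against 12.8%; "Power was set at 80%, alpha at 0.05 and a range of values for inter class correlation (ICC) between 0.01-0.2 was considered" (two-sided assumed). Randomisation units and time-periods: five hospitals, "with only one hospital being randomised each time at each step", eight periods, transition periods excluded. That leaves 5 × 8 − 5 = 35 hospital-periods. I used the design as the text describes it, with each hospital in control until its own transition. The cells as printed in Table-1 make treatment collinear with period and cannot be fitted.

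**Inputs assumed.** The SAP gives neither hospital-specific mortality nor a calendar trend. I took equally spaced hospital mortality of 14–18%, 12–20% and 8–24% around 16%, and a flat trend or odds falling by 20% or 30% over the eight periods.

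**Step 1: the plan's own figures.** 434,000 × 0.025 / 5 / 4 = 542.5, which agrees with about 540. For a linear model with hospital and period terms, the variance of the treatment coefficient is 0.6 × p(1−p)/m, where 0.6 is the treatment element of the inverse design matrix for the 35 cells. With p = 0.144 and m = 540, SE = √(0.6 × 0.144 × 0.856 / 540) = 0.0117, or 1.17 points. Power = Φ(3.2/1.17 − 1.96) ≈ 78%. With a random hospital effect it is 78.6% at ICC 0.01 and 78.1% at ICC 0.2. The stated 80% is reproduced to within 2 points.

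**Step 2: the two models do not estimate the same thing.** The design effect as an odds ratio is (0.128/0.872)/(0.16/0.84) = 0.771, a log odds ratio of −0.261. The linear coefficient in the same case is −3.2 points.

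| Baseline mortality | Risk difference if OR is 0.771 | OR if risk difference is −3.2 points |
|---|---|---|
| 8% | −1.72 | 0.58 |
| 12% | −2.49 | 0.71 |
| 16% | −3.20 | 0.77 |
| 20% | −3.85 | 0.81 |
| 24% | −4.43 | 0.83 |

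When there is an effect, the models agree only if all hospitals and periods share one mortality.

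**Step 3: standard error of the linear model.** For each of the 5! = 120 assignments of hospitals to steps, I compared the constant-variance SE with the true one, √(Σ h² p(1−p)/m), where h is the weight each cell receives in the treatment estimate. With no trend and no effect the estimate is unbiased, and type I error is 2Φ(−1.96 × model SE / true SE).

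| Hospital mortality | Model SE (points) | True SE by order (points) | Type I error by order | Mean |
|---|---|---|---|---|
| 12–20% | 1.22 | 1.18 to 1.25 | 4.3% to 5.7% | 5.0% |
| 8–24% | 1.21 | 1.13 to 1.28 | 3.7% to 6.4% | 5.0% |

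Logistic regression with fixed hospital terms gives 5.0% for every order.

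**Step 4: further dependence on the drawn order.** Suppose effects are constant in odds and odds fall 20% over the trial. With no treatment effect, the expected linear estimate stays within ±0.08 points (14–18%) or ±0.15 points (12–20%), against a standard error of about 1.1 to 1.2 points. For 12–20%, type I error is 4.3% to 5.8%, averaging 5.0%. With a true OR of 0.771 the expected estimate runs from −3.04 to −2.79 points (14–18%) or −3.15 to −2.67 (12–20%).

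Now reverse the assumption: effects constant in points, mortality 8–24%, a common fall of 4.2 points and no treatment effect. The linear model is unbiased, while fixed-hospital logistic regression gives ORs of 0.96 to 1.06 and type I error up to 7.8%.

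**Limits.** These are expected proportions with fixed hospital effects and no patient covariates, which isolates the question of scale.

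**The case against.** The fallback is fixed in advance, applies only on failure to run, cites a methods source and calls itself an approximation. The sample-size effect is itself given as a fall in mortality from 16% to 12.8%, which reads naturally as a difference in proportions. Nothing in the SAP shows that failure is likely with about 540 episodes per hospital-period. All of this stands and limits the weight of the point. It does not make a risk difference an odds ratio, and the word *approximating* describes how the model is fitted without naming the new estimand.

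A reader might go further and infer that the fallback's result depends on which hospital drew which step, as a fault peculiar to the linear model. With mortality of 8–24% and odds falling 30%, linear type I error does range from 3.8% to 8.0%, and power at an OR of 0.77 from 47% to 88% (logistic 64% to 76%). The documents do not support that reading. Those inputs are not in the SAP. The bias needs both unequal hospitals and effects constant in odds, and the mirror image appears in the logistic model if effects are constant in points. Averaged over orders in that same extreme case, linear type I error is 5.5% and power about 69%, against 70.5% for logistic. This is ordinary scale misspecification.

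**Conclusion.** The point holds as one about estimand and reporting. The fallback returns a risk difference, cannot yield the promised odds ratio for Model-3, and is wrongly called equivalent. These conclusions rest on the text alone.

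The numerical consequence is secondary and modest. The constant-variance standard error moves type I error to between 4.3% and 5.7% under a 12–20% spread in hospital mortality, or between 3.7% and 6.4% under 8–24%, with a mean of 5.0%. Both spreads are assumed. If hospitals share the same mortality and there is no trend, this part vanishes. The case for a logit-scale fallback is that the SAP chose that scale for its primary analysis, and not that the odds scale is known to be the true one. The change is worth making because it concerns the primary result, although the event that triggers it may never occur.

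**What to change.** Replace the NOTE with an ordered fallback on the logit scale:

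1. If a patient random effect is fitted and the model fails, drop it and use standard errors clustered on patient.
2. If the model still fails, fit ordinary logistic regression with hospital as five fixed indicators and the same period and patient covariates, with patient-clustered standard errors where episodes repeat. Report that odds ratio and 95% confidence interval as the primary result.

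Delete *equivalent*. Keep the linear model, if wanted, as a sensitivity analysis labelled as a risk difference, with heteroscedasticity-robust standard errors. State what counts as failure to converge, and apply the same rule to secondary outcomes 2 and 6.

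Step 2 should be fittable: 540 × 0.16 ≈ 86 deaths are expected per hospital-period in control, and there is no variance component to estimate.

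The cost is a few sentences and no data. There are two small downsides. Hospital effects are treated as fixed, which costs about half a point of power in the linear calculation above (78.1% against 78.6% at ICC 0.01). Without the patient effect, the odds ratio is no longer conditional on patient, so the clustered standard errors are needed: dropping the effect alone would ignore the within-patient correlation that the SAP provides for.
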